11.8 Safety Analyses

Safety summaries will be presented for the All-treated population, unless stated otherwise.

Sponsor: Bristol-Myers Squibb
Protocol no: IM011021

11.8.1 Adverse Events

The collection of nonserious AE information begins at initiation of study treatment and continues until the last follow-up visit. All SAEs that occur from the time the informed consent form (ICF) is signed through 30 days after the final dose of the study treatment must be reported. After that time, only SAEs deemed by the investigator to be related to the study treatment or a study procedure would be reported.

An adverse event (AE) including SAEs is defined as any new untoward medical occurrence or worsening of a preexisting medical condition in subjects that do not necessarily have causal relationship with treatment. Treatment-emergent adverse events (TEAEs) are those which first occur after the first dose of study drug or increase in severity after the first dose of study drug. The collected AEs (including SAEs) on CRF with an onset date between first dose date (including) and last dose day +30 days post last day or up to first dose day of study IM011-074 for roll over subjects will be summarized. All adverse events which change in severity or relationship to study drug are assigned a new start date and captured as a new record.

AEs will be coded according to MedDRA (version 21.0 or an updated version at the time of DBL). All adverse event tables will be summarized by treatment group and combined BMS-986165 groups.

A summary of the number and percentage of subjects reporting the following along with the number of events reported will be presented by treatment group and combined BMS-986165 groups:

- Subjects with at least one treatment-emergent adverse event
- Subjects with at least one treatment-related TEAE
- Subjects with at least one serious adverse event
- Subjects with at with one related serious adverse event
- Subjects discontinuing study drug due to an adverse event
- Subjects discontinuing study due to an adverse event
- Subjects who died

A breakdown of the number and percentage of subjects reporting each TEAE, categorized by coded body system and preferred term will be presented. Note that counting will be by subject not event and subjects are only counted once within each body system or preferred term; however, the number of total events including multiple events per subject will also be presented. A summary of treatment-related TEAEs will be provided. Furthermore, TEAEs and treatment-related TEAEs will be summarized for each preferred term in descending order.

A summary of TEAEs categorized by severity (mild, moderate, or severe) will also be provided. Events reported under multiple categories will be considered only at their maximum severity. Subjects with multiple events within a particular body system or preferred term will be counted under the category of their most severe event within that body system or preferred term.

A summary of TEAEs leading to discontinuation of study drug will be provided, grouped by body system and preferred term for all TEAEs and treatment-related TEAEs.

All adverse events (including non-treatment-emergent events) recorded on the CRF will be listed.

AE (including deaths) dates will be imputed according to algorithms detailed in [Appendix 3](#). The imputed dates will be used to assess whether AEs should be considered as treatment-emergent and included in the safety summaries. The original, partial dates will be included in data listings.

No imputation will be performed on missing AE severity or relationship, they will be left as missing.

The exposure-adjusted incidence rate (EAIR) per 100 person-years of exposure (IR/100 P-Y) is calculated as follows:

$$100 \text{ (person)} * \frac{\text{number of subjects with the specific event}}{\text{total exposure-time (in years) among the subjects of that particular treatment}}$$

where total exposure time (years) among the subjects of that particular treatment

Sponsor: Bristol-Myers Squibb
Protocol no: IM011021

$$= \sum (\text{exposure time (days) for all subjects of that particular treatment}) * \frac{1 \text{ year}}{365.25 \text{ days}}$$

Subject Exposure Time (days) is calculated as follows:

- If a subject has at least 1 event while on that particular treatment, the exposure time for that subject is:

$$\text{First AE onset date} - \text{Treatment start date (of that particular treatment)} + 1 \text{ day}$$

- If a subject does not have an event, the exposure time for that subject is:

$$\text{Treatment stop date (of that particular treatment)} - \text{Treatment start date (of that particular treatment)} + 1 \text{ day}$$

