8.3 Adverse Events

Adverse events will be reported by the subject (or, when appropriate, by a caregiver, surrogate, or the subject's legally authorized representative).

The investigator and any designees are responsible for detecting, documenting, and reporting events that meet the definition of an AE or serious adverse event (SAE) and remain responsible for following up AEs that are serious, considered related to the study treatment or the study, or that caused the subject to discontinue before completing the study.

The definitions of an AE or SAE can be found in [APPENDIX 3](#).

Contacts for SAE reporting are specified in [Appendix 3](#).

The event (term), along with its start and stop dates, maximum intensity (mild, moderate, or severe), seriousness (yes/no), relationship to the IP (yes/no), action taken with regard to the IP, and outcome will be recorded in the eCRF.

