| 
The intensity of AEs is determined by a physician and will use the following levels:
 
• Mild: An event that is easily tolerated by the subject, causing minimal discomfort, and not interfering with everyday activities.• Moderate: An event that causes sufficient discomfort and interferes with normal everyday activities.• Severe: An event that prevents normal everyday activities. An AE that is assessed as severe should not be confused with an SAE. Severe is a category utilized for rating the intensity of an event; and both AEs and SAEs can be assessed as severe. |
| Assessment of Causality |
| 
• The investigator is obligated to assess the relationship between study intervention and each occurrence of each AE/SAE. A “reasonable possibility of a relationship” conveys that there are facts, evidences, and/or arguments to suggest a causal relationship rather than a relationship cannot be ruled out.• The investigator will use clinical judgment to determine the relationship.• Alternative causes, such as underlying disease(s), concomitant therapy, and other risk factors, as well as the temporal relationship of the event to study intervention administration, will be considered and investigated.• The investigator will also consult the Investigator Brochure (IB) and/or Product Information, for marketed products, in his/her assessment.• For each AE/SAE, the investigator must document in the medical notes that he/she has reviewed the AE/SAE and has provided an assessment of causality.• There may be situations in which an SAE has occurred and the investigator has minimal information to include in the initial report to Sponsor. However, it is very important that the investigator always make an assessment of causality for every event before the initial transmission of the SAE data to Sponsor.• The investigator may change his/her opinion of causality in light of follow-up information and send a SAE follow-up report with the updated causality assessment.• The causality assessment is one of the criteria used when determining regulatory reporting requirements. |

Follow-up of AEs and SAEs

If only limited information is initially available, follow-up reports are required. Note: Follow-up SAE reports must include the same investigator term(s) initially reported.

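### SAP 11.8.1 splits an adverse event at each change in severity or causality with no rule to rejoin the records, so event counts repeat episodes and a re-dated pre-dose SAE can enter the summaries

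*SAP*

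**What the plan says.** SAP 11.8.1 sets the recording convention: "All adverse events which change in severity or relationship to study drug are assigned a new start date and captured as a new record". It covers a fall in severity as well as a rise, and a change of causality alone.

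The same section reports the number of events beside the number of subjects in its overview. In the tables by body system and preferred term it says that "the number of total events including multiple events per subject will also be presented". SAP 11.8.3 repeats this for SAEs.

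Treatment-emergent events are defined as "those which first occur after the first dose of study drug or increase in severity after the first dose of study drug". The set of events to be summarised is chosen by date: "The collected AEs (including SAEs) on CRF with an onset date between first dose date (including) and last dose day +30 days" (or, for subjects who roll over, up to the first dose of the extension study). On partial dates, SAP 11.8.1 adds: "The imputed dates will be used to assess whether AEs should be considered as treatment-emergent and included in the safety summaries".

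Protocol 8.3 lists what goes on the eCRF: "The event (term), along with its start and stop dates, maximum intensity (mild, moderate, or severe" and so on, which reads as one record per event. Protocol Appendix 3 says of SAEs that "The investigator may change his/her opinion of causality in light of follow-up information", and that the SAE report is updated when intensity or relationship changes.

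**The concern.** A count of events is useful only if one episode is one event. Here a single reaction that worsens, improves and is then re-attributed becomes four records, and nothing in the SAP puts them back together. The event-count columns would then measure how often investigators re-rated events as well as how often events happened.

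The new start date matters too. The summary window works on onset date, so a re-dated record can bring in an event that began before the first dose. SAEs are collected from consent, so such records can exist. Finally, when causality is revised, the superseded assessment survives as its own record, and the SAP does not say which assessment the treatment-related table should use.

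**Working it through.** The documents give no figure that depends on this rule, so there is nothing to reproduce. The check applies the SAP 11.8.1 rules to hypothetical records.

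**1. One on-treatment AE.** Mild on day 10, moderate on day 20, mild on day 30, causality changed from unrelated to related on day 35. There are 3 changes, so 3 + 1 = 4 records.

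| Output | Rule in SAP 11.8.1 | Result | One record per event |
|---|---|---|---|
| Number of events | all records | 4 | 1 |
| Number of subjects | once per body system or term | 1 | 1 |
| Severity table | maximum severity | moderate, once | moderate, once |
| EAIR numerator | subjects | 1 | 1 |
| EAIR exposure | first onset − treatment start + 1 | 10 − 1 + 1 = 10 days | 10 days |

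Only the event count is distorted by the repeated records.

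**2. Size over a whole table.** Let q be the share of AEs that change at all and m the mean number of changes among those. Factor = 1 + q × m. The documents give neither input, so both are assumptions.

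| q | m = 1 | m = 2 | m = 3 |
|---|---|---|---|
| 5% | 1.05 | 1.10 | 1.15 |
| 10% | 1.10 | 1.20 | 1.30 |
| 20% | 1.20 | 1.40 | 1.60 |
| 30% | 1.30 | 1.60 | 1.90 |

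**3. An SAE that begins before first dose.** Severe on day −5, improving to mild on day 8. The second record has an onset date of day 8.

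- By the TEAE definition: it neither first occurred nor rose in severity after first dose, so 0 TEAEs.
- By the onset date of the new record: 1 event in the window.

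The SAE row of the overview (11.8.1) and the SAE table (11.8.3) are not restricted to TEAEs. The onset window is their only stated filter, so this SAE enters them. It enters the TEAE tables only if the flag is programmed from the date alone. If 1 to 3 such subjects fell in an arm of about 90 and had no other qualifying event, the subject percentage would rise by 1/90 = 1.1 to 3/90 = 3.3 points. The numbers 1 to 3 are assumed. Nonserious AEs are collected only from first dose, so they do not raise this problem.

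**4. Causality.** An event judged related and later unrelated leaves two records. Counting each subject once does not help, because one related record is enough to place the subject in the treatment-related table.

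**The case against.** The case on the other side is substantial.

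- **The main safety results are protected.** Subject-level counting, the maximum-severity rule and the subject-based EAIR all have explicit rules that repeated records cannot disturb. This stands. A reader might infer that the safety tables are wrong throughout, and the SAP does not support that.
- **The TEAE definition excludes an improving pre-dose event.** This also stands. A reader might infer that the SAP makes improving pre-dose events treatment-emergent. Its definition says the opposite. The conflict arises from the onset window and date-based flagging, and concerns only SAEs that start between consent and first dose in a subject who is then randomised. The definition does not, however, protect the SAE summaries, which are not limited to TEAEs.
- **The sentence may describe data capture only.** The SAP was developed using a CRF dated 14 January 2021, which is not among the documents, and that form may link the records. Even so, the SAP needs an analysis rule that uses the link. It has such a rule for the severity table and none for event counts.
- **Keeping any related assessment is conservative.** That is a defensible choice, and the documents do not require the last assessment to govern. What is missing is a statement of the choice.
- **Unequal inflation by dose is not shown.** A reader might infer that the dose-related acneiform reactions inflate the higher-dose arms more. Protocol 2.2.2 reports acne in 15 of 17 completers at 12 mg QD, but that is an incidence in healthy subjects and says nothing about changes per event. It also describes these reactions as mild or moderate and responsive to topical treatment.

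**Conclusion.** The point holds within limits. Followed as written, SAP 11.8.1 counts an AE with k changes k+1 times in the AE and SAE event-count columns, and this does not match the recording described in Protocol 8.3 and Appendix 3. Treatment-related subject counts depend on an unstated choice between successive causality assessments. A pre-dose SAE that only improves or is re-attributed after dosing enters the SAE summaries. It would also enter the TEAE tables if flagged by date alone, against the SAP's own definition.

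The size cannot be determined from the documents. The factor of 1.05 to 1.90 rests on the assumed 5% to 30% of AEs with 1 to 3 changes. No difference between arms is established, and no efficacy result or hypothesis test depends on this.

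**What to change.** In SAP 11.8.1, and by reference in 11.8.3:

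- Link split records to the event they came from and to its original onset date, and count each linked episode once, at maximum severity.
- Treat a post-dose record of a pre-dose event as treatment-emergent only if its severity rose above the pre-dose level.
- Apply the onset window to the original onset date, or to the date of that rise.
- State which causality assessment governs the treatment-related table.
- Reconcile the recording convention with Protocol 8.3 and Appendix 3.

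The cost is SAP wording and one collapsing step in the AE analysis dataset. If the eCRF carries an identifier that ties the records together, no new data are needed. If it does not, the link would have to rest on the same preferred term with contiguous dates. That could merge distinct events, so it should have a blinded medical check before database lock.

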11.8.2 Adverse Events of Interest

Adverse events of interest (AEI) include the following:

- Skin-related AEs
- Influenza
- Herpes Zoster
- Tuberculosis
- Opportunistic/Other Infections
- Malignancy events

These events will be summarized by body system and preferred term. cSMQ defined at program level will be applied to select the AEs.

Creatine kinase (CK) elevation for CK elevation > 2.5 upper limit of normal will be summarized as CTCAE grade 2 or higher in the clinical laboratory summaries.

11.8.3 Deaths and Serious Adverse Events

The number and percentage of subjects reporting each SAE, categorized by body system and preferred term coded will be presented. Note that counting will be by subject not event and subjects are only counted once within each body system or preferred term; however, the number of total events including multiple events per subject will also be presented. A further tabulation of these events if related to the study drug, as reported on the CRF, will be provided.

All SAEs will be provided in a listing.

Adverse events with an outcome of death will be summarized.

All AEs with an outcome of death will be listed for the enrolled population.

11.8.4 Laboratory Data

Laboratory parameters will be summarized using both the International System (SI) of Units and conventional system of Units, unless otherwise specified. Summaries will be provided separately by different panels including hematology, general chemistry, chemistry - hepatobiliary, chemistry - renal function tests, chemistry - coagulation, and urinalysis. Only lab assessments with collection date up to last dose day +30 days post last dose day or up to first dose day of study IM011-074 for roll over subjects will be summarized. Data will be summarized by analysis visit, as applicable. The following summaries will be provided for each parameter:

- Absolute and change from baseline values
- Laboratory abnormalities (as determined by Controlled Terminology Criteria for Adverse Events [CTCAE v5.0] grading) presented as the worst postbaseline toxicity group

Sponsor: Bristol-Myers Squibb
Protocol no: IM011021

- Shifts from baseline to maximum postbaseline value
 - Potential drug induced liver injury (DILI) is defined as a subject who meets the following criteria on the same assessment date:
 - 1) ALT or AST elevation >3 times ULN
AND
 - 2) Total bilirubin >2 times ULN
AND
 - Normal serum alkaline phosphatase (No initial findings of cholestasis)
 - ALT or AST elevation >5 times ULN
- All abnormalities in laboratory data will be provided in listings.

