- c) Currently on any therapy for chronic infection (eg, pneumocystis, cytomegalovirus, herpes simplex, herpes zoster, invasive bacterial or fungal infections, or atypical mycobacteria)
- d) History of congenital or acquired immunodeficiency
- e) Known active infection, or any major episode of infection requiring hospitalization or treatment with parenteral (intramuscular or IV) antimicrobial agents (eg, antibiotics,

antiviral, antifungal, or antiparasitic agents) within 30 days of randomization, or completion of oral antimicrobial agents within 2 weeks of randomization

- f) Previous history of herpes zoster, herpes simplex, or influenza infection within 12 weeks before randomization or a history of disseminated/complicated herpes zoster infection (multidermatomal involvement, ophthalmic zoster, central nervous system involvement, or post-herpetic neuralgia)
- g) Administration of a live vaccine within 90 days or an inactivated vaccine within 30 days before randomization. Heat-killed or otherwise inactivated or protein vaccines (eg, influenza and pneumococcal vaccines) may be received at any time on study. Furthermore, live vaccines should not be used during treatment or within the 2 months following last dose, and any other inactivated vaccines (eg, tetanus, etc) should be used according to local guidelines during the TP.

5) Physical and Laboratory Test Findings

- a) Clinically significant abnormalities on chest X-ray or ECG
- b) Clinically significant abnormalities in laboratory tests including the following:
 - i) Serum alanine aminotransferase (ALT) $> 2 \times$ ULN, unless explicitly related to SLE
 - ii) Serum aspartate aminotransferase (AST) $> 2 \times$ ULN, unless explicitly related to SLE
 - iii) Serum total bilirubin $> 1.5 \times$ ULN, unless explicitly related to SLE or documented Gilbert's syndrome
 - iv) Hemoglobin < 8 g/dL (80 g/L) or, if due to hemolytic anemia related to SLE, < 7 g/dL (70 g/L)
 - v) Proteinuria > 3.0 g/day (3000 mg/day) or equivalent level of proteinuria as assessed by UCPR (3 mg/mg or 339 mg/mmol)
 - vi) Estimated glomerular filtration rate < 30 mL/min
 - vii) Absolute white blood cell count $< 1.2 \times 10^3/\mu\text{L}$ ($1.2 \times 10^9/\text{L}$)
 - viii) Platelet count $< 50 \times 10^3/\mu\text{L}$ ($50 \times 10^9/\text{L}$)

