8.5.3 Clinical Safety Laboratory Assessments

A central laboratory will perform assessments of safety laboratory assessments (except pregnancy tests) and provide reference ranges and laboratory reports. Investigators must document their review of each laboratory safety report. Any laboratory test result that the investigator considers clinically relevant is to be recorded on the appropriate AE page of the eCRF (Section 8.3.7). Results of clinical laboratory tests performed during screening must be available prior to randomization. Additional safety assessments may be performed at local laboratories at the investigator's discretion. The laboratory parameters to be assessed are as follows:

- Hematology: hemoglobin, hematocrit, total leukocyte count (including differential), platelet count, RBC count, and manual differential (separate smear)

- Chemistry: AST, ALT, gamma glutamyltransferase, total bilirubin, direct bilirubin, alkaline phosphatase, lactate dehydrogenase, creatinine, blood urea nitrogen, uric acid, fasting glucose, total protein, albumin, sodium, potassium, chloride, calcium, phosphorus, magnesium, creatine kinase, creatinine clearance (screening only)
- Coagulation: prothrombin time, INR, and either partial thromboplastin time or activated partial thromboplastin time
- TSH (screening only)
- Tests performed after a ≥ 10 -hour fast: lipid panel (total cholesterol, high-density lipoprotein cholesterol, low-density lipoprotein cholesterol, and triglycerides), plasma glucose
- Urinalysis: protein, glucose, blood, leukocyte esterase, specific gravity, pH; microscopic examination of the sediment if blood, protein, or leukocyte esterase are positive on dipstick; spot urine will be assessed for urine protein and urine creatinine
- Serology to be performed at screening: hepatitis C antibody, HBsAg, anti-HBc, HIV-1 and HIV-2 antibody, TB (screening only)

In addition, urine pregnancy testing will be performed for WOCBP, and follicle-stimulating hormone will be measured to confirm postmenopausal status (as applicable; at screening only).

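### Laboratory shift tables run to the maximum value for every parameter, so for blood counts no table crosses baseline grade with the worst low on-treatment grade.

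*SAP*

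**What the plan says.** SAP 11.8.4 introduces its list with "The following summaries will be provided for each parameter" and states "Summaries will be provided separately by different panels including hematology". Three of the listed summaries bear on blood counts:

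- "Absolute and change from baseline values". The section adds "Data will be summarized by analysis visit, as applicable".
- CTCAE v5.0 abnormalities, "presented as the worst postbaseline toxicity group".
- "Shifts from baseline to maximum postbaseline value".

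The section gives no shift to the minimum and no rule that depends on the parameter. It does not say that the worst-grade table is broken down by baseline grade. All laboratory abnormalities are listed. SAP 11.0 adds that continuous summaries include the minimum and first quartile, and that all data are listed by subject and visit.

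The counts concerned are in protocol 8.5.3: "Hematology: hemoglobin, hematocrit, total leukocyte count (including differential), platelet count, RBC count". Protocol 5.2, criterion 5)b), excludes white cells only below 1.2 x 10^3/uL, platelets only below 50 x 10^3/uL, and hemoglobin only below 8 g/dL (below 7 g/dL if due to SLE hemolysis).

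**The concern.** For ALT, AST, bilirubin or creatine kinase, the highest post-baseline value is the worst one. For a blood count it is the best one. A patient whose platelets collapse for two months and recover is entered in the shift table at the recovered value.

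A shift table exists to separate patients who were already abnormal from those who became abnormal or got worse. That separation matters here for three reasons.

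- The entry limits for white cells and platelets lie below the thresholds the protocol itself uses to score leukopenia (3,000) and thrombocytopenia (100,000) in the SLEDAI-2K (Appendix 11). Pre-existing cytopenia is therefore allowed.
- Protocol Appendix 9 expects the drug to be immunosuppressive, and inclusion criterion 3)a) allows it to be given with a background immunosuppressant.
- Adverse event tables are an incomplete backstop. Under protocol 8.3.3, nonserious SLE-related events are recorded on the disease instruments and not as adverse events, and cytopenia is not among the events of interest in SAP 11.8.2.

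As written, the one table built to compare a patient with his or her own baseline looks the wrong way for counts. The worst-grade table looks the right way but does not separate new cytopenia from old.

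**Working it through.** The documents give no figure for laboratory shifts, so there is none to reproduce. The check is a reading of the rule plus illustrations. Their distributions and effect sizes are assumptions, not trial data.

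**Number of values.** The protocol schedules (Tables 2 and 3) take hematology at Weeks 2, 4, 8, 12, 16, 20 and 24 (7) and at Weeks 28, 32, 36, 40, 44 and 48 (6). That is 7 + 6 = 13 scheduled on-treatment values, or 14 with the follow-up visit.

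**No drug effect.** If baseline and k post-baseline values are exchangeable, the probability that the maximum lies below baseline is 1/(k + 1). For k = 13 this is 1/14 = 7%, so 13/14 = 93% of patients shift to a value at or above baseline. For k = 14 the figure is 14/15 = 93%.

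**Transient fall.** Take independent normal values, 13 visits, and a fall of 3 SD at 4 of them. The maximum is still at or above baseline in 90% of patients and is 2 SD or more below it in 0.1%. The minimum is 2 SD or more below baseline in 95%. With no true fall, the minimum is that low in 38%, which is the noise in any minimum of 13 values.

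**Sustained fall in white cells.** Assumptions: geometric mean 5.5 x 10^3/uL, lower limit 4.0, log-SD 0.30 between and 0.15 within subjects, 13 visits, 200,000 simulated subjects. Shifts are among subjects normal at baseline; worst values are among all subjects.

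| True reduction | Normal to low, by maximum | Normal to low, by minimum | Worst value < 3.0 | Worst value < 2.0 |
|---|---|---|---|---|
| 0% | 0.16% | 30% | 12.6% | 0.7% |
| 15% | 1.9% | 54% | 26.7% | 2.8% |
| 25% | 7.3% | 71% | 41.3% | 6.4% |

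For 90 patients all normal at baseline, the 15% reduction gives 90 x 0.019 = 1.7 normal-to-low shifts by the maximum and 90 x 0.54 = 49 by the minimum. With no effect, the minimum gives 90 x 0.30 = 27.

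**Mixing of old and new.** In the same model 3.5% of subjects start below 3.0. Of those whose worst value is below 3.0, 25% were already below 3.0 at baseline with no drug effect, and 13% with the 15% reduction. The uncrossed worst-grade table cannot remove them.

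**What the other planned summaries show.** With the 15% reduction, the mean by-visit change is about -0.87 x 10^3/uL, with a standard error of about 0.13 at 90 per arm. Taking a similar standard error for placebo, the difference has standard error 0.13 x √2 = 0.18. The fall is then more than four standard errors (0.87/0.18 = 4.8).

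**One patient (invented values).** Platelets are 90 at baseline, with a lowest value of 40 and a highest of 102. The planned shift is 90 to 102, an apparent recovery above the SLEDAI-2K threshold of 100. The worst-grade table records the 40 but not that baseline was already low. The change of -50 enters only the group statistics for that visit and the listings.

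**The case against.** A reader might infer that the trial could not see a drug-related cytopenia, or that falls in counts are never set against baseline. The documents do not support that.

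- Change from baseline is planned for every parameter and visit, with the minimum and first quartile shown.
- The worst post-baseline grade is tabulated, and in the illustration above the proportion with a worst value below 3.0 about doubles (12.6% to 26.7%).
- The placebo arm is concurrent, randomized 1:1:1:1 and subject to the same entry limits. Pre-existing cytopenia is therefore expected equally in every arm. It dilutes a difference but does not create one.
- Protocol 5.2 sets what is permitted at entry. The documents do not say how common low counts are.
- Clinically significant or treatment-limiting laboratory abnormalities are captured as adverse events (protocol 8.3.7), and the data monitoring committee reviews unblinded safety data (protocol 4.1.1).

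All of this stands. It does not supply the missing table. By-visit statistics do not count patients who newly fell or worsened, listings do not compare arms, and the worst-grade table does not separate old from new.

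It can also be said that the bullet loosely means maximum toxicity grade, or that table shells would settle the direction. The first is possible, but the bullet says value where its neighbor says toxicity group, so the literal reading is the more natural one. A programmer following the text would take the maximum. If grade was meant, one clarifying line settles it.

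**Conclusion.** The point holds as a gap in safety reporting. Read literally, SAP 11.8.4 makes the shift table uninformative for falls in hemoglobin, leukocytes, neutrophils, lymphocytes and platelets. No planned categorical table then separates new or worsened cytopenia from cytopenia present at entry. It does not follow that the trial is blind to this harm: a group-level fall would be visible in the change summaries, in the worst-grade table against placebo and in the listings.

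The loss is the patient-level count by arm. In the illustration, that count barely moves by the maximum (0.16% to 1.9% for a 15% fall) and moves clearly by the minimum (30% to 54%). These percentages rest on an assumed white-cell distribution, and other inputs would change them. That a maximum over 13 visits hides transient falls does not depend on those inputs. Efficacy, power, error rates and data collection are not affected.

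**What to change.** Replace the shift bullet in SAP 11.8.4 with:

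> Shift from baseline CTCAE grade to worst post-baseline CTCAE grade in the direction of concern: lowest value for hemoglobin, leukocytes, neutrophils, lymphocytes and platelets; highest value where elevation is adverse, such as ALT, AST, bilirubin and CK; both directions for parameters graded both ways.

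Add a note that the lowest of many visits also reflects random variation, so the table is to be read against the placebo arm and not as an absolute rate. The cost is SAP wording and table shells. All the values are already scheduled for collection.
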